## 191 Inclusion Criteria

192 • Aged 18 years or over.

- Able to provide written consent.
- Travellers returning with milder symptoms suggestive of COVID-19 or returning from high risk areas requiring quarantine, as recommended by Public Health England.
- Healthcare professionals with milder symptoms suggestive of COVID-19 unable to isolate at home.

## 198 Exclusion Criteria

- Any participants that withdraw their consent.
- A skin condition/reaction preventing wearing the wearable sensor (these can be communicated by the participant to the researcher or healthcare staff at the hotel).
- The presence of a permanent pacemaker or cardiac defibrillator.
- Any form of psychiatric disorder or a condition that, in the opinion of the investigator, may hinder communication with the research team.
- Inability to cooperate or communicate with the research team.

209 Descriptive statistics will be obtained about the baseline characteristics of participants. Continuous  
210 variables will be presented as mean  $\pm$  standard deviation or medians and ranges, depending on  
211 distribution. Categorical variables will be reported as numbers and percentages. The total  
212 frequencies of alerts, proportion of actioned alerts, and resultant actions will be described.  
213 Outcome measures (e.g. phone consultation, virtual GP review, transfer to hospital) will be reviewed  
214 from case notes should escalation occur and described in absolute frequencies. Questionnaire data  
215 will be presented using frequency distributions. Data will be analysed using SPSS, Stata, and  
216 GraphPad.

217 Qualitative analyses:

218 Semi structured interviews will take place by the primary lead researcher using the prepared topic  
219 guides. An audio recording will be made of all interviews. The interviewer may also take field notes  
220 reflecting the verbal responses and reflections to be used to adapt the topic/study direction. The  
221 audio recordings will be transcribed. The data will be analysed appropriately using thematic analysis.

222 To ensure confidentiality and anonymity, each interview will be allocated a pseudonym, to be  
223 applied to the corresponding consent form, topic guide form/field notes and audio file. Their name  
224 will not be included in the audio recording; the pseudonym will be used.

225 Summaries of interview field notes will be typed into a word processor. All paper and soft copies of  
226 field notes, audio files and consent forms will be kept securely in a locker within a locked office and  
227 if in digital format, on a password protected computer and backed up regularly. Information will only  
228 be shared within the study team.

229 Audio recordings will be professionally transcribed verbatim, and a random selection of transcripts  
230 will be checked against recordings for accuracy. Interview transcripts will be analysed using Braun  
231 and Clarke's thematic analysis by two independent researchers; disagreements will be resolved  
232 through discussion. Power considerations:

233 As a pilot study in an unknown viral pandemic, the progression of which is not well established, this  
234 study will appraise the feasibility for hotel remote sensing under these circumstances. Sufficient  
235 other data do not exist to allow for power calculations.

236

237 *Patient and public involvement:*

238 Due to the nature of the pandemic and the current climate (national lockdown advised from the  
239 government) with COVID-19, patient and public involvement was not undertaken for this

240 observational trial. All eligible participants will be approached to enter the study and all recruited  
241 participants can provide email addresses should they wish for dissemination of results.

242 Discussion:

243 To the best of our knowledge, this is the first remote monitoring study focussing on healthcare  
244 delivery during a global pandemic at a remote site (i.e. hotel), acting as an extension to a healthcare  
245 trust. Apart from reducing infection risk to healthcare staff, continuous remote monitoring using a  
246 discrete wearable sensor has the potential to detect earlier clinical deterioration allowing for earlier  
247 intervention and provide further insight into the clinical course of COVID-19 in regards to vital signs.

248 Our pilot study design will test the viability of using a remote site for healthcare delivery during  
249 times of crisis. Continuous vital sign monitoring should provide insight to determine whether vital  
250 sign trends can detect clinical deterioration for COVID-19, requiring hospitalisation. Furthermore,  
251 questionnaires and semi-structured interviews of participants will provide insight into wider  
252 implementation of this technology and provide feedback for improvements. Similarly, semi-  
253 structured interviews of staff will provide a healthcare perspective, particularly thoughts on reducing  
254 potential infection risk through remote monitoring services.

255 Despite the strengths of our study, the design presents inherent limitations. Mainly, the lack of  
256 randomisation and control arm to compare remote monitoring services to 'standard care'.

257 However, to maximise capacity at the hotel given the unknown of the pandemic, a pragmatic,  
258 observational design was favoured; randomisation was not deemed appropriate. Government  
259 restrictions are rapidly changing for air travel, which could significantly alter our sample size,  
260 increasing the risk of type II errors. The inclusion of healthcare professionals may bias the  
261 description of favourable experiences, owing to their familiarity of continuous monitoring of  
262 physiological parameters. In addition, implementing remote monitoring systems entails an initial  
263 financial cost with new logistical and legal considerations; given the early phase of work, the true  
264 extent of these issues remains unknown. If the trial is proven to be feasible, this work could power

265 future randomised trials to explore for cause-effect relationships and describe cost-  
266 utility/effectiveness of remote monitoring solutions.

267 In conclusion, the results of our study would have potential to demonstrate the feasibility of remote  
268 monitoring during a pandemic and may provide insight into earlier recognition of clinical  
269 deterioration in individuals suspected with COVID-19.

270

271 **Declarations**

272 *Ethics approval and consent to participate*

273 All participants must provide consent to participate. This study has been received ethical approval  
274 by London – Queen Square Research Ethics Committee (IRAS: 281757).

275 *Consent for publication*

276 Consent will be taken for publication.

277 *Availability of data and materials*

278 The datasets used and/or analysed during the current study are available from the corresponding  
279 author on reasonable request. Only the authors have access to the dataset.

280 *Competing interests*

281 The authors declare that they have no competing interests

282 *Funding*

283 This work was supported by a grant provided through CW+ (the official charity of Chelsea and  
284 Westminster Hospital). The funding body will play no role in the design of the study and collection,  
285 analysis, and interpretation of data and in writing this manuscript.

286 *Authors' contributions*

287 FMI drafted the manuscript. Amendments were made by MJ, SK, HA, GD, and AD. Statistical  
288 considerations were discussed with MJ, SK and HA. The idea was conceived by MJ and SK.

289 *Acknowledgements*

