# Design of the pilot, proof of concept REMOTE-COVID trial: REmote MOniToring usE in suspected cases of COVID-19 (SARS-CoV 2)

## A trial protocol

[name]1\*, [name], [name], [name], [name], [name]

- 1) Division of Surgery & Cancer, [name]
- 2) West Middlesex University Hospital, [name]

Clinical trials registration information: ClinicalTrials.gov Identifier: NCT04337489

16 March 2020

16 Abstract:

17 Background: The outbreak of SARS-CoV-2 (coronavirus, COVID-19), declared a pandemic by the  
18 World Health Organisation (WHO) is global health problem with ever-increasing attributed deaths.  
19 Vital sign trends are routinely used to monitor patients with changes in these parameters often  
20 preceding an adverse event. Wearable sensors can measure vital signs continuously (e.g. heart rate,  
21 respiratory rate, temperature) remotely and can be utilised to recognise early clinical deterioration.

22 Methods: We describe the protocol for a pilot, proof-of-concept, observational study to be  
23 conducted in an engineered hotel near London airports, United Kingdom. The study is set to  
24 continue for the duration of the pandemic. Individuals arriving to London with mild symptoms  
25 suggestive of COVID-19 or returning from high risk areas requiring quarantine, as recommended by  
26 Public Health England, or healthcare professionals with symptoms suggestive of COVID-19 unable to  
27 isolate at home will be eligible for a wearable patch to be applied for the duration of their stay.  
28 Notifications will be generated should deterioration be detected through the sensor and displayed  
29 on a central monitoring hub viewed by nursing staff, allowing for trend deterioration to be noted.  
30 The primary objective is to determine the feasibility of remote monitoring systems in detecting  
31 clinical deterioration for quarantined individuals in a hotel.

32 Discussion: This trial should prove the feasibility of a rapidly implemented model of healthcare  
33 delivery through remote monitoring during a global pandemic at a hotel, acting as an extension to a  
34 healthcare trust. Potential benefits would include reducing infection risk of COVID-19 to healthcare  

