35 staff, with earlier recognition of clinical deterioration through ambulatory, continuous, remote  
36 monitoring using a discrete wearable sensor. We hope our results can power future, robust future  
37 randomised trials.

38 Trial registration: ClinicalTrials.gov Identifier: NCT04337489

39 Keywords: remote sensing technology; protocol; clinical trial; patient deterioration; monitoring,  
40 ambulatory.

41 Background:  
42 The recent outbreak of SARS-CoV-2 (COVID-19), declared a pandemic by the World Health  
43 Organisation (WHO) and a growing global health problem, has stretched resources, creating  
44 pressures within the National Health Service (NHS) with implications for patient safety. UK Chief  
45 Medical Officers have raised the risk to the UK to high, with ever increasing confirmed cases and  
46 attributed deaths.

47 High risk travellers with suspected or confirmed cases of COVID-19 are likely to transferred  
48 immediately to hospital. However, travellers with milder symptoms or returning from high risk  
49 areas, a two-week period of observation/quarantine may be required, in accordance with Public  
50 Health England recommendations. The rate of clinical deterioration for individuals suffering with  
51 COVID-19 remains unknown; given that widespread vaccine deployment remains imminently  
52 unforeseeable, novel strategies are required in approaching this pandemic.

53 Vital signs trends (heart rate, respiratory rate, blood pressure, temperature, oxygen saturations) are  
54 routinely used for monitoring hospital patients. Clinical deterioration may be recognised through  
55 changes in these parameters, and often precedes an adverse event. As such, The National  
56 Institute for Health and Care Excellence (NICE) and the Royal College of Physicians (RCP) recommend  
57 that all patients have their vital signs recorded every 12h as a minimum.

58 Across the National Health Service (NHS), the use of the National Early Warning Score 2 (NEWS), a  
59 'track and trigger' warning score, has been implemented in accordance with the RCP to guide on  
60 escalation protocols and monitoring frequency of vital signs. Accordingly, heart rate (HR),  
61 respiratory rate (RR), temperature, blood pressure, oxygen saturations, and level of consciousness  
62 are assessed every 4-6 hours with more frequent monitoring for acutely unwell patients.

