89 Feasibility will be tested through rate of participation and number of vital alerts generated.

90 The SensiumVitals™ (Sensium Healthcare Ltd., United Kingdom) system can be engineered in the  
91 building (hotel) for use with the wearable sensor. All participants would be fitted with the sensor on  
92 arrival and would always be worn. A designated area within the facility would act as a central hub  
93 allowing for remote monitoring to occur by healthcare staff. Alerts would be generated, in  
94 accordance with NEWS parameters (Table 1) but can be individually tailored, to identify  
95 deteriorating participants. Participants can be escalated to hospitals should rapid deteriorating in  
96 vital signs be noted; ambulance services and paramedics will be present on site to facilitate this. The  
97 decision to escalate will come from a senior nurse, present on site, or a general practitioner  
98 contactable at all times.. The temperature alert threshold was lowered to the lowest score in the  
99 NEWS chart, allowing for earlier detection and improved sensitivity; this decision was made from  
100 previous work which demonstrated varying limits of agreement for temperature when compared to  
101 nursing observations. Escalation protocols will be developed and trialled, allowing staff to address  
102 issues as they arise (Figure 1).

103 *Wearable sensor system*  
104 SensiumVitals™ by the Surgical Company, have produced a lightweight, waterproof, single-use,  
105 wearable wireless ‘patch’ with a battery life of 5 days measuring vital signs every two minutes. The  
106 sensor attaches to an individual’s chest with two ECG electrodes, recording HR, RR, and a wire  
107 attaches around the individual’s back, measuring axillary temperature. The sensor is FDA approved  
108 and CE marked. Data are transmitted through radiofrequency and dedicated intranet hotspots.  
109 Physiological parameters can be viewed by clinical staff on a mobile device/desktop computer,  
110 allowing trends towards deterioration to be noted, with tailored alerts generated for deteriorating  
111 individuals in accordance with NEWS (Figure 2).

112 All sensor data collected by the SensiumVitals® system will be stored on a created secured hotel  
113 network; access to which is restricted to research personnel. Given that the hotel acts as an

114 extension to a healthcare trust, the SensiumVitals® system inherits all the hospital procedures and  

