## 166 *Outcomes and progression criteria:*

## 167 Feasibility outcomes:

1. Rate of participation  
Using the confidence interval approach, for a minimum sample size of 10 individuals, we estimate a rate of participation of 90% with a 95% confidence interval of +/- 18%.
2. Generation of an alert following abnormal vital signs (e.g. raised temperature).  
We aim for a minimum of 5 vital alerts to be generated to demonstrate feasibility.
3. Missing data recorded from sensor limited to less than 20% attrition will be a criterion for progression.
4. Number of adverse events relating to the sensor system (e.g., skin reaction to sensor preventing trial continuation)

178 Exploratory clinical outcomes:

1. Actions following alert generation (e.g., phone consultation, virtual general practitioner review, transfer to hospital).
2. Acceptability and usability of the SensiumVitals™ system by healthcare staff and participants (mixed methods analysis)

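### Withdrawal of consent is listed as an exclusion and nothing visible keeps early leavers in the denominator of the <20% missing-data criterion; applied literally, this could tilt the criterion towards feasible

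*Combined protocol and SAP*

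**What the plan says.** The Exclusion Criteria open with "Any participants that withdraw their consent". The next entry is "A skin condition/reaction preventing wearing the wearable sensor". Sequence of events, step 2, places consent on arrival, for the sensor then to be applied.

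Under Feasibility outcomes, item 3 reads "Missing data recorded from sensor limited to less than 20% attrition will be a criterion for progression". Item 4 is "Number of adverse events relating to the sensor system (e.g., skin reaction to sensor preventing trial continuation". Item 1 gives its precision "for a minimum sample size of 10 individuals".

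On intended wear, the Abstract describes a "wearable patch to be applied for the duration of their stay", and Overall design has the sensor fitted on "arrival and would always be worn".

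The visible statistical text after the Exclusion Criteria is descriptive. It defines no analysis set, gives no rule for withdrawals or missing data, and does not say whether the 20% is a share of people, of planned-stay time or of worn time. Lines 206 to 208, just before that text, are absent from the extracted document, so this statement covers the visible text only.

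**The concern.** Consent cannot be withdrawn before it is given, so the first criterion has no screening reading: it acts on people who have already enrolled. The skin criterion is partly ordinary screening, since a pre-existing condition that prevents wear is a proper exclusion. Its wording also reaches a reaction to the worn sensor.

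People who stop early are the ones who lose most sensor data. If they are excluded and so leave the item 3 calculation, the criterion is judged only on those who tolerated the sensor and kept it on. In a feasibility study of wearing a sensor, that removes much of what the criterion should measure. The Discussion warns that travel restrictions could alter the sample size significantly, so a sample near the minimum, where two people matter, is possible.

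**Working it through.** **The plan's own figures.** The 20% has no derivation to reproduce. The only computable figure nearby is item 1's half-width: 1.96 × √(0.9 × 0.1 / 10) = 18.6%, against the stated 18%. It does not enter the checks below.

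**Inputs.** From the documents: the 20% limit, the minimum of 10, and, to convert shares of a stay into days, the Background's "a two-week period of observation/quarantine may be required". No stay length is given for healthcare professionals, so 14 days for everyone is an assumption. The documents give no number of leavers, stop time or background missingness. I assume one or two leavers and a background of 5%, 10% or 15%.

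**1. Share of people.** Attrition = k/n with leavers kept, and 0/(n − k) with leavers dropped.
- n = 10, k = 2: 2/10 = 20%, which is not below 20%, so it fails; dropped, 0/8 = 0%, which passes.
- n = 10, k = 1: 10% or 0%; passes either way.
- With everyone kept, failure needs 2 of 10, 3 of 15 or 4 of 20. With leavers dropped, they can never cause a failure.

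**2. Share of planned-stay time.** Let b be background missingness, the same for everyone while wearing the sensor; let k of n people stop after a share s of equal planned stays.
- Kept: M = b + (k/n)(1 − b)(1 − s). Dropped: M = b. The difference, (k/n)(1 − b)(1 − s), is never negative, so dropping can only lower the figure.
- n = 10, k = 2, b = 0.10, dropped: 10.0%. Kept:
  - stop on day 1 of 14: 0.10 + 0.18 × 13/14 = 26.7%, fails
  - day 5: 0.10 + 0.18 × 9/14 = 21.6%, fails
  - day 7: 0.10 + 0.18 × 7/14 = 19.0%, passes
- Break-even: s = 1 − (0.20 − b) / [(k/n)(1 − b)]. For n = 10, k = 2:
  - b = 0.05: 1 − 0.15/0.19 = 21% of the stay
  - b = 0.10: 1 − 0.10/0.18 = 44%, about day 6 of 14, or day 3 if the stay were 7 days
  - b = 0.15: 1 − 0.05/0.17 = 71%
- n = 10, k = 1, worst case s = 0: 14.5%, 19.0% and 23.5% at b = 0.05, 0.10 and 0.15. Only the 15% background can reverse the result.
- n = 15, k = 2, b = 0.10: at most 0.10 + (2/15) × 0.90 = 22.0%, reversing only before 1 − 0.10/0.12 = 17% of the stay.
- n = 20, k = 2, b = 0.10: at most 0.10 + 0.10 × 0.90 = 19.0%; no reversal.

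**3. Share of worn time.** n = 10, two stops on day 5, 10% gaps in the other eight, gap rate g in the leavers while worn: M = (8 × 14 × 0.10 + 2 × 5 × g) / (8 × 14 + 2 × 5) = (11.2 + 10g)/122.
- g = 0: 9.2%; g = 0.10: 10.0%; g = 0.30: 11.6%. Dropped: 10.0%.
- The effect is small, can go either way, and passes throughout.

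**The case against.** The strongest reply is that the Exclusion Criteria are an eligibility list, not an analysis rule. They do not say that an excluded person's data leave item 3, so the harmful step is inferred. That stands as a limit: the documents show a rule that biases the figure if followed literally, not an announced intention to follow it that way. It does not remove the point, because the withdrawal criterion has no other role at screening and no visible text rules the literal reading out.

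The skin criterion is the weaker part. Item 4 already treats a reaction that stops participation as an event in a participant, and the criterion can be read as screening at the initial assessment. This largely stands. It still sets no denominator for item 3, and withdrawal for other reasons is untouched by it.

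Item 3 speaks of data from the sensor, so a headcount rests mainly on the word *attrition*. This is fair. Wear for the whole stay supports planned-stay time better, but does not fix it.

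Reversal needs several things together: literal exclusion, a unit other than worn time, a sample near 10, and usually two early leavers. Ten is a minimum tied to item 1, and the study is meant to run for the whole pandemic. All of this stands and limits the size of the point. Text on data after withdrawal could also lie in the absent lines or in consent pages that were removed from the document.

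**Conclusion.** The point holds in conditional form and rests mainly on withdrawal of consent. If the exclusions are applied literally and the 20% is a share of people or of planned-stay time, item 3 is biased towards feasible. At the minimum sample, two leavers can change the result; in larger samples the same two matter less, and on a worn-time reading the bias is not established. The stop counts, stop times, background rates, equal stays and 14-day length are all assumptions.

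Three stronger readings are tempting and not supported:
- A reader might infer that the sponsor plans to discard leavers. The text leaves this open.
- A reader might treat item 3 as deciding progression alone. The plan calls it one criterion and does not say that failing it stops progression.
- A reader might infer that skin reactions would vanish from outcome 4. Excluding a person after a reaction and still counting the event are compatible.

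**What to change.** - Limit the exclusion criteria to conditions present before fitting, keeping a pre-existing skin condition that prevents wear.
- Treat withdrawal of consent and on-study skin reactions as discontinuations. This concerns how people are counted, not when a sensor should come off. Reactions remain counted under outcome 4.
- State that everyone fitted with a sensor stays in the denominator of outcome 3, using data up to withdrawal as consent allows.
- State the unit of the 20% before data are examined. The choice is the sponsor's; if it is worn time, report the number of people who stop early beside it, because worn time alone does not show them.

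The cost is protocol wording, with no extra participants or procedures. The downside is that the missing-data figure may look less favourable.

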## 346 Figure legends:

347 Figure 1: Potential escalation pathway; NEWS: National Early Warning Score; GP: general

348 practitioner.

349 Figure 2: Monitoring system for SensiumVitals™ Wearable Sensor

350 Table:

351 *Table 1: Criteria for generating vitals alert*

Parameter	Alert threshold
Respiratory rate (breaths per minute)	$\geq 25$
Temperature (Celsius)	$\geq 38.1$
Heart rate (beats per minute)	$\geq 131$

352
